5 STUDY ENDPOINTS

5.1 PRIMARY EFFICACY ENDPOINT

The Ishak Fibrosis Score will be determined by liver biopsy as scored by the central histopathologist. The Ishak Fibrosis Score classification is defined as:

- 0 = No fibrosis (F0);
- 1 = Fibrous expansion of some portal areas, with or without short fibrous septa (F1);
- 2 = Fibrous expansion of most portal areas, with or without short fibrous septa (F2);
- 3 = Fibrous expansion of most portal areas, with occasional portal to portal bridging (F3);
- 4 = Fibrous expansion of portal areas, with marked bridging (F4);
- 5 = Marked bridging with occasional nodules (F5);
- 6 = cirrhosis probable or definite (F6).

Fibrosis scores of F0 and F1 will be excluded from enrollment. The change from baseline in the Ishak Fibrosis Score will be derived for each subject and will be used to classify subjects into one of the three following groups:

- Improvement, defined as having a reduction from baseline of at least 1-point in the Ishak Fibrosis Score
- Stable, defined as having no change from baseline in the Ishak Fibrosis Score
- Worsening, defined as having an increase from baseline in the Ishak Fibrosis Score

Subjects will be classified as a responder or non-responder based on the above three groups and their baseline Ishak Fibrosis score. The definition of response is based on the following:

- For subjects with baseline Ishak Fibrosis Score of F2-F5, achieving either improvement or remaining stable
- For subjects with baseline Ishak Fibrosis Score of F6, achieving improvement

The response at Month 24 will be used as the primary endpoint in this study. Response rates at Month 12 using the same definitions as above will also be summarized.

5.2 SECONDARY EFFICACY ENDPOINTS

5.2.1 Ishak Modification of Knodell Histological Activity Index

The Ishak modification of Knodell histological activity index will be determined by liver biopsy. The four items and their categorizations scores include:

- interface hepatitis
 - 0 = None
 - 1 = Mild (local, few portal areas)
 - 2 = Mild/moderate (focal, most portal areas)
 - 3 = Moderate (continuous around <50% of tracts or septa)

- 4 = Severe (continuous around >50% of tracts or septa)
- confluent necrosis
 - 0 = None
 - 1 = Focal confluent necrosis
 - 2 = Zone 3 necrosis in some areas
 - 3 = Zone 3 necrosis in most areas
 - 4 = Zone 3 necrosis + occasional portal-central bridging
 - 5 = Zone 3 necrosis + multiple portal-central bridging
 - 6 = Panacinar or multiacinar necrosis
- parenchymal injury (focal lytic necrosis, apoptosis and focal inflammation)
 - 0 = None
 - 1 = One focus or less per 10× objective
 - 2 = Two to four foci per 10× objective
 - 3 = Five to ten foci per 10× objective
 - 4 = More than ten foci per 10× objective
- portal inflammation
 - 0 = None
 - 1 = Mild, some or all portal areas
 - 2 = Moderate, some or all portal areas
 - 3 = Moderate/marked, all portal areas
 - 4 = Marked, all portal areas

The Ishak modification of Knodell histological activity index will be assessed at months 12 and 24.

5.2.2 NASH CRN Fibrosis Stage Scoring

In order to provide a potential comparison to how fibrosis improvement would be viewed in a traditional paired biopsy study in NASH, the Ishak fibrosis scores will be mapped to a comparable fibrosis stage in the NASH CRN staging system. The NASH CRN fibrosis stage classification is defined as: 0=None (F0); 1a=mild, Zone 3, perisinusoidal fibrosis (F1); 1b=moderate, Zone 3, perisinusoidal fibrosis (F1); 1c=portal/periportal fibrosis only (F1); 2=perisinusoidal and portal/periportal fibrosis (F2); 3=bridging fibrosis (F3); and 4=cirrhosis (F4). To map Ishak Fibrosis Score to the NASH CRN definitions, Table 2 will be used to map the scores from Ishak to NASH CRN:

Table 2. Mapping of fibrosis staging from Ishak to NASH CRN

Ishak Fibrosis Scoring	NASH CRN Mapped Score
F0	F0
F1	F1
F2	F2
F3	F3
F4	F3
F5	F4

F6	F4
----	----

The proportion of patients who have at least a one stage improvement in the mapped fibrosis stages will be evaluated at Month 12 and Month 24.

5.2.3 Clinical Outcomes

Clinical outcomes will be documented from a blinded medical review of MedDRA coded AEs collected from the eCRF prior to database lock. Clinical outcomes will include decompensation events, re-transplantations, and all-cause mortality. Decompensations events will include variceal bleeding, hepatic encephalopathy, ascites, hepato-renal syndrome, and jaundice. The following specific MedDRA coded preferred terms to be used are:

- Liver Transplant, Kidney Transplant
- Death
- Oesophageal varices haemorrhage
- Hepatic encephalopathy
- Ascites
- Hepatorenal syndrome
- Jaundice

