8.6.2 Completion of the Study

The Investigator will document the completion or the reason for early withdrawal by a subject in the case report form. The following categories should be used to describe the early withdrawal reasons in the case report form:

- Subject discretion (document reason)
- Investigator considers it to be in the best interest of the subject (document reason)
- Adverse event(s)
- Administrative reasons (e.g., early termination of the study)
- Subject lost to follow-up
- Major protocol violation (with approval by the Sponsor)
- Death

If the study is prematurely terminated by Conatus, all reasonable attempts should be made to complete the final follow-up phase for all remaining subjects.

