12.2.2 Efficacy Variables

The following parameters will be recorded for the efficacy evaluation:

- Histologic changes defined as ≥ 1 point change in the Ishak Fibrosis Score
- Effects on liver inflammation in the necro-inflammatory sub-score of the modified Histological Activity Index. A responder will be defined as a subject who has improved by at least 2 points at 24 months on the necro-inflammatory sub-score of the modified Histological Activity Index from Baseline.
- Clinical outcomes defined as time to clinical worsening. Time to decompensation, re-transplantation, and/or death will be captured as clinical outcomes. (Note: Decompensation is defined as presence of: bleeding varices, encephalopathy, ascites requiring treatment and jaundice.)
- Effects on biomarkers of apoptosis and mechanism of action
- Effects on liver function parameters such as ALT, AST, bilirubin
- Changes in transient elastography (at select centers)

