13.2 Adverse Event Definitions

The following definitions of terms are guided by the International Conference on Harmonization and the U.S. Code of Federal Regulations [21 CFR 312.32] and are included herein.

An adverse event is any untoward medical occurrence associated with the use of a drug in humans, whether or not considered drug related.

Adverse events include, but are not limited to:

- Any symptom or condition not previously reported by the subject (medical history).
- An exacerbation of a pre-existing symptom or condition.
- A significant increase in frequency or intensity of a pre-existing episodic event or condition.
- A drug interaction.
- A condition first detected or diagnosed after study drug administration even though it may have been present prior to the start of the study.

An AE does **not** include:

- Medical or surgical procedures (e.g., surgery, endoscopy, tooth extraction, or blood transfusion); the condition that leads to the procedure is an adverse event (e.g., bleeding esophageal varices, dental caries).
- Overdose of either study drug or concurrent medication without any clinical signs or symptoms.

Suspected adverse reaction means any adverse event for which there is a reasonable possibility that the drug caused the adverse event. For the purposes of safety reporting, 'reasonable possibility' means there is evidence to suggest a causal relationship between the drug and the adverse event. A suspected adverse reaction implies a lesser degree of certainty about causality than adverse reaction, which means any adverse event caused by a drug.

Title: A Multicenter, Double-Blind, Randomized Trial of IDN-6556 in Subjects Who had Hepatitis C Virus (HCV) Reinfection and Liver Fibrosis or Cirrhosis following Orthotopic Liver Transplantation for Chronic HCV Infection and Who Subsequently Achieved a Sustained Virologic Response Following anti-HCV Therapy

An adverse reaction is any adverse event caused by a drug. Adverse reactions are a subset of all suspected adverse reactions for which there is reason to conclude that the drug caused the event.

An adverse event or suspected adverse reaction is considered “serious” if, in the view of either the Investigator or sponsor, it results in any of the following outcomes:

- Death
- A life-threatening adverse event
- Inpatient hospitalization or prolongation of existing hospitalization

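### SAP 5.2.3 looks for re-transplantation and death under AE preferred terms that the protocol's AE rules do not require sites to record, so the clinical-outcome table may undercount both.

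*SAP*

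**What the plan says.** Protocol 12.2.2 names the outcomes: "Time to decompensation, re-transplantation, and/or death will be captured as clinical outcomes". It does not say on which form they are collected.

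SAP 5.2.3 keeps the same three kinds of event ("Clinical outcomes will include decompensation events, re-transplantations, and all-cause mortality") and names one source: "Clinical outcomes will be documented from a blinded medical review of MedDRA coded AEs collected from the eCRF prior to database lock". It then narrows the source to a list, introduced by "The following specific MedDRA coded preferred terms to be used are". The list has eight terms:

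- two transplant terms on one line, "Liver Transplant, Kidney Transplant";
- 'Death';
- five decompensation conditions: variceal haemorrhage, hepatic encephalopathy, ascites, hepatorenal syndrome and jaundice.

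SAP 9.2.4 summarises each outcome descriptively by treatment group, through Month 12 and through Month 24. No test is specified.

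Protocol 13.2 governs what reaches the AE data. Among the things an AE does not include, it lists "Medical or surgical procedures (e.g., surgery, endoscopy, tooth extraction, or blood transfusion); the condition that leads to the procedure is an adverse event". Death appears in the same section under a different rule: an AE is serious when, "in the view of either the Investigator or sponsor, it results in any of the following outcomes", and death is the first outcome listed.

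**The concern.** The SAP searches the AE data for terms that a site following the protocol has no instruction to enter. A re-transplantation is a surgical procedure, so the site records the condition that led to it. A death is the result of an event, so the site records that event. In either case the preferred term on the SAP's list need not appear, and the list contains no term for a failing graft or for a cause of death outside decompensation.

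These are the hardest outcomes in the trial, and the table carries more weight than its descriptive status suggests. Protocol 12.6.3 counted death and re-transplantation as progression within the primary analysis. SAP 5.1 defines response from the Ishak score alone and does not carry that component over. SAP 9.2.4 is therefore the only place where re-transplantation is summarised as an outcome. SAP section 4 says the development decision will also consider the secondary efficacy analyses, and this table is one of them.

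**Working it through.** No figure in the plan is at issue, so the check sets the sections side by side and then looks for any other source for the same events.

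**Step 1. Classify the eight terms in SAP 5.2.3 against Protocol 13.2.**

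| Terms | Number | Status under Protocol 13.2 |
|---|---|---|
| Liver Transplant, Kidney Transplant | 2 | Procedures, excluded from the AE definition |
| Death | 1 | Not excluded; an outcome of an AE |
| Decompensation conditions | 5 | Conditions, reportable as AEs |

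2 + 1 + 5 = 8. The first two rows depend on terms that the AE rules do not lead a site to enter. The third row is unaffected.

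**Step 2. Is there another source for re-transplantation?**

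- The Schedule of Events (Protocol Appendix I) has a row for adverse events and none for clinical outcomes.
- Protocol 8.6.2 introduces the withdrawal reasons with "The following categories should be used to describe the early withdrawal reasons in the case report form". Re-transplantation is not among them.
- SAP 14.1 and 14.2, on changes in planned analysis, do not mention the conflict.
- Protocol 13.5.2 requires SAE follow-up reports with hospital records. A re-transplant could be recognised there, but SAP 5.2.3 does not point to them.

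No alternative source is named.

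**Step 3. Is there another source for death?** There is.

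- 'Death' is a withdrawal reason in Protocol 8.6.2.
- SAP 8.1 tabulates the reason for study withdrawal by treatment group.
- SAP 11.2 plans a listing of subjects who died. It also refers to AE outcome as a data field when it says how missing values are handled.

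None of these is named in SAP 5.2.3 as a source for the clinical-outcome table. Protocol 13.5.1 asks the investigator to establish a diagnosis if possible, which makes coding to the cause more likely. One report could therefore show fewer deaths in the outcome table than in the disposition table or the death listing.

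**Step 4. Size of one missed subject.** With the planned arms of 20 placebo and 40 emricasan subjects (Protocol Table 7.1):

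- placebo: 1/20 = 5 percentage points;
- emricasan: 1/40 = 2.5 percentage points.

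Neither document gives an expected rate of death or re-transplantation, so the number of missed events cannot be estimated.

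**The case against.** The strongest reply is that little is lost. SAP 5.2.3 opens with a blinded medical review, and a physician reading the AE data may recognise a re-transplant or a fatal event whatever its preferred term. Sites may also enter a transplant as an AE despite the definition. Deaths are recorded and reported elsewhere in the same study. The table is descriptive, and neither the response definition in SAP 5.1 nor the thresholds in SAP section 4 use it.

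Most of this stands, and it sets the limits of the point. What it does not answer is that the fixed list makes no provision for recognising events outside it, and that no other source for re-transplantation is named.

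A reader might also infer more than the documents support:

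- *The table will miss these events.* The documents support 'may miss', for the reasons above.
- *The procedure exclusion explains the death gap.* It does not. Death is not a procedure and is not excluded. That gap arises from coding a fatal event to its cause.
- *The trial will lose its mortality data.* SAP 8.1 and 11.2 report deaths by other routes. The risk is an inconsistent count in one table.
- *Kidney transplants will inflate the count.* The procedure exclusion would keep them out of the AE data too. The SAP also does not say that a kidney transplant counts as a liver re-transplantation; the two terms only share a line. What remains is that the entry is unexplained. Protocol 7.2 excludes anyone with a previous renal transplant, so an on-study kidney transplant would be a first one.

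**Conclusion.** The point holds in limited form. SAP 5.2.3 and Protocol 13.2, each followed as written, can undercount re-transplants and deaths in the SAP 9.2.4 table. For re-transplantation the cause is a direct conflict, with no other source named. For death it is a mismatch between a preferred term and an outcome, and data already planned for collection can repair it.

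The size is 5 or 2.5 percentage points per missed subject, depending on the arm, for an unknown number of subjects that may be zero. The decompensation terms, the sample size and the Month 24 primary analysis are unaffected.

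The conclusion assumes that sites apply the AE definition as written and that the listed terms decide what is counted. That a re-transplant would be coded to a term such as graft failure is an assumption, since neither document states the coding conventions.

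**What to change.** Amend SAP 5.2.3 before database lock.

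1. **Deaths.** Derive them from any AE or SAE with a fatal outcome plus the 'Death' withdrawal reason. Reconcile the result with the listing in SAP 11.2, allowing for the table's Month 24 cut-off.
2. **Liver re-transplantation.** Extend the planned blinded medical review beyond the fixed list to all AEs and SAEs that could underlie a re-transplant, such as graft failure, together with their SAE documentation. The withdrawal record cannot supply this, because re-transplantation is not a listed reason.
3. **Kidney transplant.** Report any such event separately from liver re-transplantation, or state why it is in the list.

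The cost is SAP wording and slightly more review of blinded data in a step that is already planned. No new assessment of subjects is needed.

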13.5 Recording and Reporting Adverse Events

13.5.1 Recording Adverse Events

All adverse events will be recorded in the appropriate section of the case report form. Subjects withdrawn from the study due to adverse events will be followed by the Investigator until the outcome is determined and, when appropriate, additional written reports and documentation will be provided. The Investigator should attempt, if possible, to establish a diagnosis based on the presenting signs and symptoms.

If the adverse event meets the definition of a serious adverse event, or if the Investigator becomes aware of an unexpected adverse event that places the subject at risk or a pregnancy at any time after the study drug administration up to the end of the study follow-up period, the event must be documented and reported as described in **Section 13.5.2**.

Title: A Multicenter, Double-Blind, Randomized Trial of IDN-6556 in Subjects Who had Hepatitis C Virus (HCV) Reinfection and Liver Fibrosis or Cirrhosis following Orthotopic Liver Transplantation for Chronic HCV Infection and Who Subsequently Achieved a Sustained Virologic Response Following anti-HCV Therapy

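### SAP 5.2.3 looks for re-transplantations and deaths under adverse-event terms that the protocol's recording rules would normally not produce, so the clinical-outcomes table may under-count them

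*SAP*

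**What the plan says.** SAP 5.2.3 defines the scope: "Clinical outcomes will include decompensation events, re-transplantations, and all-cause mortality". It names one source: "Clinical outcomes will be documented from a blinded medical review of MedDRA coded AEs collected from the eCRF prior to database lock". It then narrows the search: "The following specific MedDRA coded preferred terms to be used are". The list has one entry reading "Liver Transplant, Kidney Transplant", one for death, and five for decompensation. SAP 9.2.4 summarises each outcome descriptively by treatment group, through Month 24 and through Month 12.

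The protocol's intention for these events is in section 12.2.2: "Time to decompensation, re-transplantation, and/or death will be captured as clinical outcomes".

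Three protocol rules decide what reaches the adverse-event data:

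- Section 13.2 lists, among things that are not adverse events, "Medical or surgical procedures (e.g., surgery, endoscopy, tooth extraction, or blood transfusion); the condition that leads to the procedure is an adverse event".
- Section 13.2 calls an event serious when "in the view of either the Investigator or sponsor, it results in any of the following outcomes", and death is the first outcome named.
- Section 13.5.1 says: "The Investigator should attempt, if possible, to establish a diagnosis based on the presenting signs and symptoms".

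**The concern.** A term-based search works only if the recording rules put the term into the data. For transplantation the protocol tells sites not to record the procedure as an event. For death it points them towards the illness that was fatal. The SAP then searches for the procedure and for the word death.

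Death and re-transplantation are the hardest outcomes in this trial. Protocol 12.6.3 counted both as progression in the primary analysis. The SAP 5.1 response definition no longer mentions them, which leaves 9.2.4 as the SAP's only efficacy summary by arm that names them. SAP section 4 says secondary efficacy and safety feed the broader assessment around the three-category guideline. With 40 and 20 subjects planned per arm, one or two events left out could change how the table reads.

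**Working it through.** The documents give no expected number of deaths or re-transplantations, so there is no planned figure to reproduce. The check sets the search rule against the recording rules.

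**Re-transplantation.**
1. Rule searched: an adverse event coded to liver (or kidney) transplant (SAP 5.2.3).
2. Rule for recording: the procedure is not an event; the condition leading to it is (Protocol 13.2).
3. Result: a site that follows the protocol enters the graft condition. No row carries the transplant term, and the list finds nothing. It succeeds only where a site departs from 13.2.
4. Backstop: re-transplantation is not a withdrawal category in Protocol 8.6.2 and has no listing in SAP 11.2.

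**Death.**
1. Rule searched: an adverse event coded to death.
2. Rules for recording: death is an outcome that makes an event serious (13.2), and a diagnosis is to be attempted if possible (13.5.1).
3. Result: a death with a known cause may be coded to that cause and missed. This is an inference; neither section says how a fatal event must be coded.
4. Backstop: death is a withdrawal reason (Protocol 8.6.2), withdrawal reasons are tabulated by arm (SAP 8.1), and subjects who died are listed (SAP 11.2). The SAP does not say that any of these feeds 9.2.4.

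**Kidney transplant.** Protocol 7.2 (criterion 2) excludes a history of renal transplant. A kidney transplant during the study would therefore be a first one, not a re-transplantation, yet it shares the list entry with liver transplant.

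**Can the loss be sized?** Let w be the share of these outcomes that are re-transplantations, q_tx the share of re-transplantations entered under a transplant term, and q_d the share of deaths coded to death. Before any help from the blinded review:

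share counted = w × q_tx + (1 − w) × q_d

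All three inputs are assumptions. With strict adherence to 13.2, q_tx = 0:

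| w | q_d = 0.1 | q_d = 0.5 | q_d = 0.9 |
|---|---|---|---|
| 0 | 10% | 50% | 90% |
| 0.25 | 0.75 × 0.1 = 7.5% | 0.75 × 0.5 = 37.5% | 0.75 × 0.9 = 67.5% |
| 0.5 | 0.5 × 0.1 = 5% | 0.5 × 0.5 = 25% | 0.5 × 0.9 = 45% |

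If sites enter half of the transplants anyway (q_tx = 0.5, w = 0.5, q_d = 0.5), the share is 0.25 + 0.25 = 50%. The range runs from 5% to 90%, and the documents do not locate the trial within it.

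**The case against.** The best defence is the blinded medical review. SAP 5.2.3 puts it first, and SAP 11.2 shows that adverse-event records carry outcome and treatment-required fields. A physician reading those records could see a fatal outcome whatever the coded term. Deaths also appear in the disposition table and the death listing, so a discrepancy would be visible. The eCRF is not in the documents, so a dedicated field cannot be ruled out. The output is one descriptive table with no hypothesis test.

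Much of this stands, and it limits the size of the point. It does not remove it. The SAP states which terms are to be used and does not say that the review may go beyond them or how the two interact. If the review does go further, the rule applied is not the one specified. The death listing would expose a mortality mismatch but does not correct the table, and re-transplantation has no equivalent check.

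A reader might infer that most of these outcomes would go uncounted, or that the table would show zero re-transplantations whatever happened. The documents do not support either. The first needs event and coding frequencies that are not given. The second needs every site to follow 13.2 and the review to add nothing. Nor do the documents show that every death with a recorded cause would be missed: the request for a diagnosis is qualified, and nothing forbids death as a reported term.

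**Conclusion.** The mismatch is real. For re-transplantation it follows from the text: if sites follow Protocol 13.2 and the SAP list is applied as written, the events are missed. For deaths with a known cause it is a reasonable inference, and they may be missed. The SAP 9.2.4 table could then under-count and contradict the disposition table and the listing of deaths in the same report.

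The number affected cannot be determined. It depends on site compliance, on how fatal events are coded, and on how far the blinded review departs from the list.

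Severity is moderate. The table is a descriptive secondary summary; alpha, power, the primary analysis and the three-category thresholds do not change.

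**What to change.** In SAP 5.2.3:

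- Derive all-cause mortality from any of: a fatal adverse-event outcome, death as the seriousness criterion, or death as the withdrawal reason. Reconcile the result with the listing of subjects who died before database lock.
- Identify re-transplantation in the planned blinded review from all adverse-event records, including the outcome and treatment-required fields and the serious-event reports, rather than from the preferred term alone. The documents do not show whether the treatment-required field names the procedure, so the review should not rely on that field by itself.
- Report kidney transplant separately from liver re-transplantation.
- Keep the preferred terms for the decompensation events.

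The cost is SAP wording, programming and slightly more blinded review before lock. The documents already show the adverse-event outcome field (SAP 11.2), the seriousness criterion in the initial serious-event report (Protocol 13.5.2) and the withdrawal reason (Protocol 8.6.2), so the mortality part should need no new data collection.
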